6.2 Secondary Efficacy Endpoints

The secondary efficacy endpoint is the change from Baseline to the end of the study where the Baseline is defined as the last observation prior to the first dose, Visit 3. The effect of SPN-810 will be measured on the following efficacy scales administered at visits designated in the Schedule of Visits and Procedures (Table 1).

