6.2.3.4 Child Health Questionnaire Parent Form 28-Item (CHQ-PF28)

The Child Health Questionnaire Parent Form 28-item (CHQ-PF28) is a short generic measure of health status and health related quality of life (Landgraf 1996). CHQ-PF28 items have four, five, or six response options, divided over eight multi-item scales (physical functioning, general behavior, mental health, self-esteem, general health perceptions, parental impact: emotional, parental impact: time, and family activities) and five single item concepts (role functioning: emotional/behavior, role functioning: physical, bodily pain, family cohesion, and change in health). The CHQ-PF28 should be performed by the primary caregiver.

The CHQ-PF28 will be administered at Visit 3 and Visit 7.

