6.2.3.5 Stress Index for Parents of Adolescents (SIPA)

The Stress Index for Parents of Adolescents (SIPA) is a screening and diagnostic instrument that identifies areas of stress in parent–adolescent interactions, allowing examination of the relationship of parenting stress to adolescent characteristics, parent characteristics, the quality of the adolescent–parent interactions, and stressful life circumstances in parents of adolescents (11-19 years old). The SIPA consists of 90 items divided in three major domains, the Adolescents Domain (AD), the Parent Domain (PD) and the Adolescent-Parent Relationship Domain (APRD), which include the following subscales: moodiness/emotional lability, social isolation/withdrawal, delinquency/antisocial, failure to achieve and persevere, relationship with spouse/partner, social alienation and incompetence/guilt. The SIPA includes 22 item Life Stressors (LS) Scale and the Index of Total Parenting Stress (TS).

Parents respond to the first 90 items using a 5-point rating scale ranging from *Strongly Disagree* (5) to *Strongly Agree* (1) and the final 22 items by indicating *Yes* (Y) or *No* (N).

The SIPA will be administered at Visit 3 and Visit 7.

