9.2 Secondary Efficacy Analyses

9.2.1 Key secondary endpoints are:

1. Change from Visit 3 to Visit 7 in the Investigator-rated CGI-S score

- 2. Change from Visit 3 to Visit 7 in R-MOAS score
- 3. R-MOAS remission rate at Visit 7

9.2.2 Additional secondary endpoints:

- 1. Actual Investigator CGI-I score at Visit 7 and change from Visit 4
- 2. Actual Caregiver CGI-I score at Visit 7 and change from Visit 4
- 3. Change from Visit 3 to Visit 7 in the Caregiver-rated CGI-S score
- 4. Change from Visit 3 to Visit 7 in the SNAP-IV ADHD scores in:
 - a. Inattention ratings
 - b. Hyperactivity/Impulsivity ratings
 - c. ODD ratings
 - d. Combined scale ratings
- 5. Change from Visit 3 to Visit 7 in the CHQ-PF28 score
- 6. Change from Visit 3 to Visit 7 in the SIPA scores in:
 - a. Adolescents domain
 - b. Parent domain
 - c. Adolescents-Parents Relationship domain
 - d. Life Stressor domain

Each of the secondary endpoints will be analyzed using a Mixed-Effect Model for Repeated Measure (MMRM). MMRM assumes missing data as Missing at Random. The model includes treatment, visit, and interaction between treatment and visit as fixed factors, baseline as covariate. The model parameters will be estimated using restricted maximum likelihood method with unstructured variance-covariance matrix and Kenward-Roger approximation to estimate denominator degrees of freedom. The between-group comparison will be performed using the simple contrast at the respective visits. The least squares mean of the treatment group, the difference in the least squares mean (SPN-810 minus placebo), and the 2-sided 95% CI for the difference will be obtained.

To preserve the overall type I error rate at 0.05 for the secondary endpoints, only SPN-810 treatment group is significantly different from placebo for the primary endpoint will be tested for secondary endpoints.

The ordering of the three (3) key secondary endpoints from first to be tested to third is: Investigator-completed Clinical Global Impression – Severity Scale (CGI-S) (Endpoint 1); Retrospective Modified Aggression Scale (R-MOAS)(Endpoint 2); Retrospective Modified Aggression (R-MOAS) remission (Endpoint 3).

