# **6.3** Additional Secondary Endpoints

The absolute value of investigator-rated Clinical Global Improvement (CGI-I) scale, Caregiver-rated CGI-I scale and Caregiver-rated CGI-S scale will be summarized the same way as for CGI-S described in the above Section.

The CGI-I is evaluated on a 7-point scale, where 1 = Very much improved, 2 = Much improved, 3 = Minimally improved, 4 = No change,5 = Minimally worse,6 = Much worse, and 7 = Very much worse.

The absolute Caregiver-rated CGI-S scale score and change from baseline will be summarized the same as for CGI-S as described above.

With respect to CHQ-PF28, z-score will be derived and be summarized by treatment group at visit 1 and 7. The recorded score needs to be transformed in 0-100 range before calculating subscales and summary scores.

CHQ-PF28 Questionnaire Item	Recorded on CRF	Final Raw	Transformed Score
1.1;	1	5	((Final -1)/4) * 100
5.2;	2	4.4	
9.4	3	3	
	4	2.2	
	5	1	
2.1a-2.1c;	1	1	((Final -1)/3) * 100
3.1;	2	2	

3.2;	3	3	
9.2	4	4	
4.1	1	6	((Final -1)/5) * 100
	2	5	
	3	4	
	4	3	
	5	2	
	6	1	
5.1a-5.1c;	1	1	((Final -1)/4) * 100
6.1a-6.1c;	2	2	
8.1a-8.1c; 9.3a-9.3b	3	3	
	4	4	
	5	5	
	1	5	((Final -1)/4) * 100
7.1a-7.1c;	2	4	
8.2; 9.1a-9.1b	3	3	
	4	2	
	5	1	

The physical functioning (PHS) and psychosocial health (PSS) summary scores are calculated in three steps.

• Step1: z-score standardizations.

Subscale	Sum of items	Formulas for z-score standardizations
Physical Functioning (PF)	2.1a-2.1c	PF_Z=(PF - 90.8525408) / 16.3826344
Role/Social Limitations - Physical (RP)	3.2	RP_Z=(RP - 91.4951246) / 18.9079749

General Health Perceptions (GH)	8.1a-8.1c,1.1	GH_Z=(GH - 66.6958379) / 19.3564297
Bodily Pain/Discomfort (BP)	4.1	BP_Z=(BP - 78.6833515) / 20.7355708
Role/Social Limitations - Emotional/Behavior (REB)	3.1	REB_Z=(REB - 90.4013015) / 19.5067502
Parental Impact - Time (PT)	9.2a-9.2b	PT_Z=(PT - 83.8816188) / 20.2901603
Parental Impact - Emotional (PE)	9.1a-9.1b	PE_Z=(PE - 73.9788476) / 21.406013
Self-Esteem (SE)	7.1a-7.1c	SE_Z=(SE - 79.2555314) / 17.8308361
Mental Health (MH)	6.1a-6.1c	MH_Z=(MH - 77.2595806) / 13.6861999
Behavior (BE)	5.1a-5.1c,5.2	BE_Z=(BE - 72.3086051) / 17.1447913
Family Activities (FA)	9.3a-9.3b	NA
Global Health (GGH)	1.1	NA
Global Behavior (GBE)	5.2	NA
Family Cohesion (FC)	9.4	NA
Change in Health (CH)	8.2	NA

• Step 2. PHS and PSS raw scores

+ (BE Z \* .27911)

• Step 3. Transformation of PHS\_raw and PSS-raw

Transformed physical (PHS) = 50 + (PHS raw \* 10)

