Transformed psychosocial (PSS) = 50 + (PSS raw \* 10)

More details can be found in the Child Health Questionnaire (CHQ) Scoring and Interpretation Manual (HealthActCHQ).

The ratings from the SNAP-IV scale are grouped into the following 4 subscales:

• ADHD-Inattention (items #1-9),

- ADHD-Hyperactivity/Impulsivity (items #10-18)
- ADHD-Combined subscales (items #1-18)
- Oppositional Defiant Disorder (ODD) (items #19-26)

Each subscale score is calculated by averaging the items scores within each subscale.

The absolute and change from baseline for SNAP-IV will be summarized by treatment group at visit 7.

Stress Index for Parents of Adolescents (SIPA) rating scale includes 112 items. The first 90 items use a 5-point rating scale ranging from Strongly Disagree (5) to Strongly Agree (1): 1=SD (Strongly Disagree), 2=DA (Disagree), 3=NS (Not Sure), 4=A (Agree), and 5=SA (Strongly Agree).

Note: Items 2, 3, 4, 5, 9, 10, 15, 25, 28, 34, 40, 45, 49, 54, 66, 69, 74, 81, 83, 85, 87, and 88 are rated from Strongly Disagree (5) to Strongly Agree (1). To be consistent with other items, they have to be reversed  $(1 \rightarrow 5, 2 \rightarrow 4, 3 \rightarrow 3, 4 \rightarrow 2, \text{ and } 5 \rightarrow 1)$  prior to calculating subscales and domains.

Domain	Subscale	Sum of Items	
Adolescent	Moodiness/Emotional Lability (MEL)	10 items (1, 6, 11, 16, 21, 26, 31, 36, 41, 46)	
Domain (AD)	Social Isolation/ Withdrawal (ISO)	10 items (2, 7, 12, 17, 22, 27, 32, 37, 42, 47)	
	Delinquency/Antisocial (DEL)	10 items (3, 8, 13, 18, 23, 28, 33, 38, 43, 48)	
	Failure to Achieve or Persevere (ACH)	10 items (4, 9, 14, 19, 24, 29, 34, 39, 44, 49)	
Parent Domain (PD)	Life Restrictions (LFR)	10 items (51, 52, 55, 56, 59, 63, 67, 71, 75, 79)	
	Relationship with Spouse/Partner (REL)	9 items (60, 64, 68, 72, 73, 76, 77, 80, 81)	
	Social Alienation (SOC)	7 items (53, 54, 57, 58, 61, 65, 69);	
	Incompetence/Guilt (INC)	8 items (62, 66, 70, 74, 78, 82, 86, 90)	
Adolescent- Parent Relationship Domain (APRD)		16 items (5, 10, 15, 20, 25, 30, 35, 40, 45, 50, 83, 84, 85, 87, 88, and 89)	

AD = MEL + ISO + DEL + ACH

PD = LFR + REL + SOC + INC

Total Parenting Stress (TS) = AD + PD + APRD

The last 22 items (91-112) with responses of 1=Yes and 0=No.

Life Stressors (LS) = Sum of last 22 items (Items 91-112)

TS, each domain, each subscale, and LS scale will be summarized by treatment group at visit 3 and 7 using descriptive statistics for continuous variable as described in Section 5.1.

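### SAP 6.3 gives no Visit 3 to Visit 7 change for SIPA or CHQ-PF28, the endpoints Protocol 9.2.2 defines, and it summarizes CHQ-PF28 at a visit where it is not collected

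*SAP*

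**What the plan says.** Protocol 6.2 sets the general rule: "The secondary efficacy endpoint is the change from Baseline to the end of the study", with Visit 3 as baseline. Protocol 9.2.2 applies it to both scales: "Change from Visit 3 to Visit 7 in the CHQ-PF28 score", and "Change from Visit 3 to Visit 7 in the SIPA scores in" four domains (adolescent, parent, adolescent-parent relationship, life stressors).

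Both questionnaires are scheduled only at those two visits. Protocol 6.2.3.4 says "The CHQ-PF28 will be administered at Visit 3 and Visit 7" and Protocol 6.2.3.5 says "The SIPA will be administered at Visit 3 and Visit 7". Table 1 agrees in both documents.

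SAP 6.3 then specifies, for SIPA, "TS, each domain, each subscale, and LS scale will be summarized by treatment group at visit 3 and 7 using descriptive statistics", and for CHQ-PF28, "z-score will be derived and be summarized by treatment group at visit 1 and 7". Neither sentence mentions change. For SNAP-IV the same section says "The absolute and change from baseline for SNAP-IV will be summarized by treatment group at visit 7".

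**The concern.** The protocol's endpoint is a difference within each subject. The SAP's output for these two scales is a pair of cross-sectional summaries. A table with an early row and a late row invites the reader to subtract one from the other, but that subtraction gives the endpoint only if the same subjects stand behind both rows. Nothing in the SAP ensures this: SAP 5.1 summarizes non-missing values and SAP 5.7 substitutes nothing for missing ones. Even with complete data, the median, quartiles and SD of the change cannot be read from two separate visit summaries.

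CHQ-PF28 has a simpler and more basic problem. The SAP names a visit at which the questionnaire is not administered, so there is no early value to summarize, let alone to subtract.

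**Working it through.** The plan states no figure for these two scales. Its sample-size calculation concerns the diary endpoint and is not in question here.

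**1. Scales whose endpoint Protocol 9.2.2 defines through change from Visit 3** (CGI-I is left out because it already rates change against baseline)

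| Scale | Post-screening collection | SAP summary | Change specified in SAP? |
|---|---|---|---|
| Investigator CGI-S | Visits 3–7 | 6.2, by visit | Yes |
| R-MOAS (score) | Visits 2–8 | 6.2, by visit | Yes |
| Caregiver CGI-S | Visits 3–7 | 6.3 | Yes |
| SNAP-IV | Visits 3, 7 | 6.3, Visit 7 | Yes |
| CHQ-PF28 | Visits 3, 7 | 6.3, Visits 1 and 7 | **No** |
| SIPA | Visits 3, 7 | 6.3, Visits 3 and 7 | **No** |

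SNAP-IV, CHQ-PF28 and SIPA share one schedule, yet only SNAP-IV gets a change score. SAP 5.1 lists the summary statistics and defines baseline, but has no general rule that adds change scores.

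**2. CHQ-PF28.** No Visit 1 value exists under either Table 1. The SAP 5.1 fallback to a screening value does not help, because none is collected for this scale. Read literally, the early row has n = 0.

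**3. SIPA: what the two rows can show when nobody changes.** Within one arm, let d be the share of analyzed subjects with a Visit 3 value but no Visit 7 value. Let g be their Visit 3 mean minus that of subjects with both values, in SD units.

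- Visit 3 row = M + d × g, where M is the Visit 3 mean of those with both values.
- Visit 7 row, with no change in anyone = M.
- Difference of rows = −d × g. Paired change = 0.

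Inputs: Protocol 9.3 assumes about 20% dropout. That is a planning figure used here for d as an illustration only. The documents give no value for g, so a range is shown.

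| d | g = 0.25 | g = 0.5 | g = 0.75 | g = 1.0 |
|---|---|---|---|---|
| 0.10 | −0.025 | −0.05 | −0.075 | −0.10 |
| 0.20 | −0.05 | −0.10 | −0.15 | −0.20 |
| 0.40 | −0.10 | −0.20 | −0.30 | −0.40 |

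A negative g reverses every sign, and g = 0 removes the shift.

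**4. Simulation check.** One arm of 93 was simulated 4,000 times. The chance of leaving (about 20% overall) rose with the Visit 3 score, and there was no true mean change. The difference of visit means averaged −0.14 SD and the paired change 0.00.

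**5. Between arms.** The shift in the SPN-810 minus placebo contrast is −(d₁g₁ − d₀g₀), with subscript 1 for SPN-810 and 0 for placebo. If both products equal 0.10, it is 0. Only attrition that differs between arms leaves a residue.

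**The case against.** Several points on the other side are sound.

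- **The efficacy set is narrower than all subjects.** SAP 6 restricts it to subjects in the safety population with enough baseline and post-baseline diary data. Leavers without usable diary data are absent from both SIPA rows, so 20% total dropout is not strictly the right d. It may be smaller; on the other hand, the halt may have cost further Visit 7 assessments. The actual figure is not given.
- **Gap and direction are assumed.** A reader might infer that attrition will make SIPA look improved. The documents do not support that: they give no Visit 3 profile of leavers, and the shift could go either way or be nil.
- **The trial is randomized.** A reader might also infer a biased treatment comparison. Attrition that is similar in both arms largely cancels there, and nothing in the documents points to differential attrition.
- **The problem is partly visible and recoverable.** The tables will show n and missing counts, and subject listings would let a reader derive each change by hand.
- **The size is small.** With about 75 completers per arm (150/2, from Protocol 9.3), the standard error of one arm's Visit 7 mean is 1/√75 = 0.115 SD, larger than the 0.10 SD mid-range shift. No test or interval is planned for these scales.
- **The SAP may supersede the protocol's methods.** Protocol 8.1 says so. The same section requires changes to principal features to go into an amendment, and the SAP nowhere states that change was dropped for these two scales.

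These points limit the consequences. They do not supply the missing change score or a CHQ-PF28 value at Visit 1.

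**Conclusion.** The point holds as a mismatch between protocol and SAP. As written, SAP 6.3 never summarizes the defined SIPA and CHQ-PF28 endpoints, and its CHQ-PF28 baseline visit contradicts its own Table 1. Both conclusions rest on the text alone.

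The attrition effect is a secondary, conditional argument that applies to SIPA within an arm. It is 0.05 to 0.20 SD if 20% of analyzed subjects lack Visit 7 and the Visit 3 gap is 0.25 to 1.0 SD, both assumptions, in either direction. It does not apply to CHQ-PF28 as written, where there is no early row to compare.

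The consequence is modest. These are the last two of six additional secondary endpoints, they are summarized descriptively, and the study was halted. SAP 5.1 even confines the analysis to primary, key secondary and safety data, which does not fit with section 6.3 being there at all. A reader might see a deliberate choice to withhold change for these scales; the documents show only an unexplained omission.

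**What to change.** In SAP 6.3:

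1. Replace the CHQ-PF28 visits (1 and 7) with Visits 3 and 7.
2. Add a sentence such as: *For the SIPA domains and Life Stressors scale named in Protocol 9.2.2, and for the CHQ-PF28 scores, within-subject change (Visit 7 minus Visit 3) will be tabulated by treatment group for subjects with both values, giving n and the Visit 3 values of those same subjects.*
3. Reconcile SAP 5.1 with 6.3: either extend the stated scope to the additional secondary endpoints, or state that they are not analyzed and why.

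The added sentence is limited to the SIPA domains that the protocol names; change in the total score and individual subscales is optional. The paired summary removes the artefact of comparing different subjects, but not all bias from informative dropout. That is why n and the matched Visit 3 values should accompany it.

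The cost is SAP wording and a few extra table columns. Both visits are already in the schedule, so no new data are needed.

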### 7 SAFETY ANALYSES

### **7.1** Adverse Events

AEs will be coded using MedDRA Version 18.1.

Adverse events will be categorized by MedDRA system organ class (SOC) and/or preferred term. A subject experiencing the same AE multiple times will only be counted once for that preferred term. Similarly, if a subject experiences multiple AEs within the same SOC, that subject will be counted only once for that SOC.

## 7.1.1 Treatment-emergent Adverse Events

Overview of Treatment-emergent adverse events (TEAEs) will be provided. The incidence of TEAEs will be summarized by MedDRA SOC, preferred term and severity. The number and percentage of subjects who experienced at least one TEAE will be tabulated by treatment group.

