9.5.1 Adverse Events

AEs will be classified into standardized medical terminology from the verbatim description (Investigator term) using the Medical Dictionary for Regulatory Activities (MedDRA). AEs will be summarized using discrete summaries at the subject and event level by system organ class and preferred term for each group of doses. Similarly, treatment-emergent AEs will be summarized by severity and relationship separately. Verbatim description and all MedDRA level terms, including the lower level terms, for all AEs will be contained in the subject data listings.

All AEs occurring throughout the study period will be recorded. Treatment-emergent AEs (TEAEs) will be collected starting after the first dose of study medication (after Visit 3) to the end of the study. These AEs include those that emerge during treatment or worsen in severity during treatment. These AEs will be tabulated, listed, and analyzed.

Separate TEAE incidence tables will be presented for the two treatment groups. The incidence rates for all SADRs will also be summarized as described for all TEAEs.

In addition, these same tables will be presented by treatment period (Titration, Maintenance, and combined Titration and Maintenance). For the combined Titration and Maintenance Periods, the incidence of TEAEs will also be presented by highest severity reported and the dose of SM at first occurrence. Listings (and tabular summaries, if warranted) of deaths, other SAEs, and other significant TEAEs, including TEAEs resulting in treatment discontinuation, will be provided.

9.5.2 **C-SSRS**

C-SSRS outcomes will be summarized using number and percent of subjects by categories for suicidal ideation only, suicidal behavior only and suicidality (ideation and behavior combined). The summary will be presented by treatment group. The proportion of subjects in each treatment group will be compared with the proportion of subjects in the placebo group using Fisher's exact test or Chi-square test as applicable if appropriate.

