#### 2 STUDY OBJECTIVES

The primary objective of this study is to assess the efficacy and safety of flexible doses of SPN-810 (36 to 54 mg/day) in the improvement of IA behaviors in adolescents diagnosed with ADHD when taken in conjunction with standard ADHD treatment.

The key secondary objectives, additional secondary objectives and exploratory objectives are to assess the effect of SPN-810 on the key secondary endpoints, additional secondary endpoints and safety endpoints described below.

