### **5 STATISTICAL METHODS and ANALYSES**

#### **5.1** General Considerations

Because SPN-810 did not show efficacy for the Treatment of Impulsive Aggression in the two previous Double-Blind Studies (810P301 and 810P302), the conduct of this study (810P503) was halted. Therefore, the analysis will be limited to the primary, key secondary endpoints and safety data, which will include adverse events (AEs), Extrapyramidal Symptoms (EPS), Simpson-Angus Scale, Barnes Akathisia Scale, and Abnormal Involuntary Movement Scale, clinical laboratory evaluations, vital signs, suicidal symptoms (C-SSRS) and ECG results.

All descriptive statistical analyses will be performed using SAS (Version 9.4), unless otherwise noted and will be presented by treatment groups (Placebo, SPN-810).

Continuous variable summaries will include the number of subjects (n) with non-missing values, mean, standard deviation (SD), median, interquartile range (Q1 and Q3), minimum, and maximum.

Categorical variable summaries will include the frequency and percentage of subjects who are in the category or each possible value. In general, the denominator for the percentage calculation will be based upon the total number of subjects in the study population for the treatment groups, unless otherwise specified. The denominator for by visit displays will be the number of subjects in the relevant study population with non-missing data at each study visit.

In general, the baseline value for a variable is defined as the last observation prior to the first dose of double-blind study medication, ideally Visit 3, but including the screening value, if necessary.

All data will be presented in Listings.

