## **5.6** Study Drug Exposure

Duration of exposure in days will be calculated from the first and last dates of the study drug administration. The duration of exposure will be calculated as date of last dose minus date of first dose + 1. Duration of exposure (days) will be summarized by categories and descriptive statistics. The categories for duration of exposure are Weeks 1-2 (Titration period), Weeks 3-5 (Maintenance Period).

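### SAP 7.1.1 omits, without explanation, the protocol's TEAE tables by treatment period and by dose at first occurrence, so dose enters no planned safety table

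*SAP*

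**What the plan says.** The SAP's primary objective is to "assess the efficacy and safety of flexible doses of SPN-810 (36 to 54 mg/day" in adolescents with ADHD. Protocol 9.5.1 matched its adverse event tables to that objective in two ways. First, "these same tables will be presented by treatment period (Titration, Maintenance, and combined Titration and Maintenance". Second, for the combined period, "the incidence of TEAEs will also be presented by highest severity reported and the dose of SM at first occurrence".

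The SAP's corresponding sentence, in 7.1.1, is "The incidence of TEAEs will be summarized by MedDRA SOC, preferred term and severity". SAP 5.1 sets the grouping for its analyses: they "will be presented by treatment groups (Placebo, SPN-810". On exposure, SAP 5.6 states "The duration of exposure will be calculated as date of last dose minus date of first dose + 1", then "Duration of exposure (days) will be summarized by categories and descriptive statistics", and finally "The categories for duration of exposure are Weeks 1-2 (Titration period), Weeks 3-5 (Maintenance Period".

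Protocol 8.1 makes the SAP take precedence over the protocol on statistical methods, so what the SAP leaves out is not planned for the report.

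**The concern.** This is a flexible-dose trial. Under protocol 4.3.2.2 and 5.4.1, subjects are titrated to 36 mg/day over two weeks and stay there for the first maintenance week. They may then move to 45 mg/day at Visit 5, and to 45 or 54 mg/day at Visit 6. Dose and time on study therefore rise together, and the investigator decides who escalates.

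A TEAE incidence by arm alone cannot show whether an event such as EPS began during titration, at 36 mg/day or after an increase. Without a count of subjects at each dose level, a reader of the tables also cannot tell whether the active arm was mainly a 36 mg/day arm or mainly an escalated one. The protocol's two breakdowns were the part of the safety analysis that spoke to this. Their loss matters because safety is what the cut-back SAP still undertakes to report.

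**Working it through.** The documents give no figure for this point, so the check is a comparison of texts followed by one illustration.

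**Step 1: the planned safety outputs side by side.**

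| Item | Protocol | SAP |
|---|---|---|
| TEAEs by period | Titration, Maintenance, combined (9.5.1) | None (7.1.1) |
| TEAEs by highest severity | Yes, combined period (9.5.1) | Severity kept, by arm, no period (7.1.1) |
| TEAEs by dose at first occurrence | Yes, combined period (9.5.1) | None (7.1.1 to 7.1.5) |
| AEs of special interest (EPS and neuroleptic malignant syndrome) | Reported on a dedicated form (6.4.3.2) | By SOC and preferred term (7.1.5) |
| EPS rating scales | Changes from baseline by visit (9.5.3) | Summarised and listed by arm (7.6) |
| Exposure | Calendar days, by period (8.7) | Calendar days, bands for Weeks 1-2 and 3-5 (5.6) |
| Tablet compliance | Categories and descriptive statistics, by period (8.7) | No summary |
| Subjects at each dose level | Not planned | Not planned |

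No SAP safety table uses dose, and no SAP adverse event table uses period.

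**Step 2: does the halt explain the omission?** SAP 5.1 limits the analysis to the primary endpoint, the key secondary endpoints and safety, because the two earlier double-blind studies did not show efficacy. Adverse events and EPS are named as retained. Nothing there says that the period or dose tables are dropped. The cut is also not applied evenly: SAP 6.3 still gives full scoring rules for CHQ-PF28, SNAP-IV and SIPA, which lie outside the scope stated in 5.1.

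**Step 3: can SAP 5.6 stand in for dose?** Inputs are the dose steps in protocol 5.4.1 and the three-week maintenance period in protocol 4.3. Assume three weeks of exactly 7 days, no missed doses and no dose reduction.

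- 36 mg/day throughout: 36 × 21 = 756 mg.
- 36 mg/day, then 45 mg/day for two weeks: 36 × 7 + 45 × 14 = 252 + 630 = 882 mg. Ratio 882/756 = 1.17.
- 36, 45, then 54 mg/day: 36 × 7 + 45 × 7 + 54 × 7 = 252 + 315 + 378 = 945 mg. Ratio 945/756 = 1.25.

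All three subjects have the same last-minus-first-plus-one duration and fall in the same band. SAP 5.6 cannot separate them, although their maintenance totals differ by up to 25% on this nominal schedule.

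**The case against.** Several points against the concern are sound.

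- **Listings.** A reader might infer that the report will carry no dose information on safety of any kind. The documents do not support that. SAP 5.1 promises listings of all data and SAP 7.1.5 subject listings of AEs, so dose at onset should be recoverable subject by subject if the dosing records are listed. The SAP names no dose field and gives no rule for assigning dose at onset, so listings soften the gap but do not close it.
- **Other AE outputs.** A reader might also infer that adverse events are collapsed into a single table. They are not. SAP 7.1.1 to 7.1.5 also plan an overview, relatedness, SAEs, TEAEs leading to discontinuation and AEs of special interest, and 7.6 covers the EPS scales. None of these uses dose or period.
- **Exposure definition.** The calendar-day formula is the protocol's own (8.7), and the SAP bands keep a coarse titration/maintenance split. Counts by dose level were never in the protocol, so asking for them is a new request.
- **Shares of treatment days.** It is tempting to say what fraction of Days 1 to 45 was spent at each dose. The documents do not allow it. Subjects converting to the open-label study are moved to 36 mg/day, which is inside the objective's range. The protocol synopsis sends AEs with onset after Visit 7 to the open-label report for subjects who enrol there. The active titration doses are not shown in Table 2. Seven days at 54 mg/day is nominal, since Visit 7 may fall up to 9 days after Visit 6. The number of completers in the halted study is not stated.
- **Context.** The study was halted and the SAP is entitled to replace the protocol's methods. By-dose tables will be sparse, and confounded by time and by investigator choice. On this view a sentence recording that the tables were dropped would be enough.

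The last point shows that the omission is not a breach. It does not supply the missing sentence, and it does not apply to the by-period tables, which depend on dates and not on anyone's choice of dose.

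**Conclusion.** The concern holds in a limited form. Two pre-specified TEAE breakdowns, by period and by dose at first occurrence, are missing from the SAP without explanation, and so is the protocol's compliance summary. SAP 5.6 offers no dose-level view of exposure. Dose is thus in no planned safety table and at most in listings, for an objective about the safety of 36 to 54 mg/day.

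The effect on any safety result cannot be calculated from the documents. The 25% difference in maintenance drug intake is an illustration of what calendar-day exposure hides; it rests on nominal weeks, full compliance and no dose reduction. No efficacy result and no type I error statement is affected. The change is worthwhile mainly because it is cheap and was already planned.

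**What to change.** In SAP 7.1.1, restore the protocol 9.5.1 tables: TEAEs by arm for Titration, Maintenance and combined and, for the combined period, by highest severity and by total daily dose at first occurrence. State how dose at onset is assigned. Label the by-dose table descriptive, because the investigator chose the dose and it rises with time.

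In SAP 5.6, restore the protocol 8.7 compliance summary. As a small addition beyond the protocol, give by arm the number and percent of subjects at each dose level (for placebo, the matching step) after Visits 4, 5 and 6.

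If the sponsor prefers to leave any protocol table out, the SAP and the study report should say which and why.

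The cost is SAP wording and a few tables, built from AE and dosing data that the protocol already collects. The drawback is small by-dose cells that must not be read as dose-response evidence.
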